**Table 4: In Case the Study is Performed at the Northern Hemisphere Only**

Number of Events at End of First RSV Season	Interim Analysis	Primary Analysis

<18 events*
	
The Interim Analysis will be conducted by the IDMC.
 
 
1. Calculate the number of events observed (cases based on case definition #2). Suppose x events were observed.
 
2. In case the study is expanded to a second season (Cohort 2), based on the initial assumptions (2000 additional subjects, with 0.75% RSV incidence and expected 70% VE), 9 additional events are expected during the second season.
 
3. Based on 1 and 2, obtain the estimated proportion of events already observed (<math>P_{IA} = x/(x+9)</math>) at the interim analysis and calculate the information fraction (IF) of the interim and the primary analysis. The IF, in this case is a 2-component vector containing the estimated proportion of events already observed at the interim analysis and the expected proportion of events at primary analysis (which is 1), so <math>IF = (P_{IA}, 1)</math>
 
4. Using this estimated IF and the Pocock’s rule, divide the full alpha (<math>\alpha = 0.05</math>) over the two planned analyses (Interim and Primary Analysis) resulting in equal significance cut-offs. This is <math>\alpha'</math> to be used at the IA.
 
5. This calculated <math>\alpha'</math> will be divided across the 3 primary endpoints based on the observed incidence of the 3 case definitions using Pocock rule. If <math>n_1, n_2</math> and <math>n_3</math> are the number of events per CD1, 2 and 3, then the corresponding <math>IF = (n_1/n_3, n_2/n_3, 1)</math> will be used to divide <math>\alpha'</math> across the 3 endpoints. The use of the Pocock rule results in equal adjusted significance cut-offs for each CD.
 
	
If Interim Analysis is positive or Interim Analysis is negative and Conditional Power < 60% then:
 
The same <math>\alpha'</math> will be used and equally divided across the 3 primary endpoints based on the observed incidence of each endpoint using Pocock rule. If <math>n_1, n_2</math> and <math>n_3</math> are the number of events per CD1, 2 and 3, then the corresponding <math>IF = (n_1/n_3, n_2/n_3, 1)</math> will be used to equally divide <math>\alpha'</math> across the 3 endpoints. The use of the Pocock rule results in equal adjusted significance cut-offs for each CD.
 
If Interim Analysis is negative and Conditional Power <math>\geq 60\%</math> then:
 
 
1. Calculate number of events observed throughout both seasons (x events observed in season 1 and y events observed in season 2) and the corrected IF of the interim and the primary analysis, so <math>IF = (x/(x+y), 1)</math>
 
2. The remaining alpha will be spent using a user defined alpha spending function approach based on the <math>\alpha'</math> that was already spent and the corrected IF of step 1. This is <math>\alpha''</math>
 
3. The new calculated <math>\alpha''</math> will be equally divided across the 3 primary endpoints based on the observed incidence of the 3 case definitions using Pocock rule. If <math>n_1, n_2</math> and <math>n_3</math> are the number of events per CD1, 2 and 3, then the corresponding <math>IF = (n_1/n_3, n_2/n_3, 1)</math> will be used to equally divide <math>\alpha''</math> across the 3 endpoints. The use of the Pocock rule results in equal adjusted significance cut-offs for each CD.
 


\*Number of RT-PCR confirmed RSV-mediated LRTD cases (based on Case Definition #2 based on the PPE).

**Table 5: In Case the Study is Performed at the Northern and Southern Hemisphere**

Timepoint/ Number of Events	Interim Analysis 1	Interim Analysis 2	Primary Analysis

Time point 1 or Time point 2 / <math>\geq 14</math> events*
	
The Interim Analysis will be conducted by the IDMC.
 
 
Calculate the number of events observed (cases based on case definition #2). Suppose x events were observed.
 
Based on epidemiological/disease transmission modeling and real-world evidence (RWE) (Attachment 2) obtain the estimated number of events expected until the end of the SH season 1. Suppose y additional events are expected.
 
Based on 1 and 2, obtain the estimated proportion of events already observed (<math>P_{IA} = x / (x + y)</math>) at the interim analysis and calculate the information fraction (IF) of the interim and the primary analysis. The IF, in this case is a 2-component vector containing the estimated proportion of events already observed at the interim analysis and the expected proportion of events at primary analysis (which is 1), so <math>IF = (P_{IA}, 1)</math>
 
Using this estimated IF and the Pocock's rule, divide the full alpha (<math>\alpha = 0.05</math>) over the two planned analyses (Interim and Primary Analysis) resulting in equal significance cut-offs. This is <math>\alpha'</math> to be used at the IA.
 
This calculated <math>\alpha'</math> will
 
	
No second interim analysis
	
If Interim Analysis 1 is positive, then:
 
The same <math>\alpha'</math> will be used and equally divided across the 3 primary endpoints based on the observed incidence of the 3 case definitions using Pocock rule. If <math>n_1, n_2</math> and <math>n_3</math> are the number of events per CD1, 2 and 3, then the corresponding <math>IF = (n_1/n_3, n_2/n_3, 1)</math> will be used to equally divide the alpha across the 3 endpoints. The use of the Pocock rule results in equal adjusted significance cut-offs for each CD.

		
No second interim analysis
	
If Interim Analysis 1 is negative but at the end of the SH RSV season <math>\geq 18</math> events* are observed:
 
 
Calculate number of events observed until the end of the SH RSV season (x observed at the time of the interim analysis and n additional events observed until the end of the SH RSV season). The corrected IF of the interim and the primary analysis is <math>(x / (x + n), 1)</math>.
 
The remaining alpha will be spent using a user defined alpha spending function approach based on the <math>\alpha'</math> that was already spent and the corrected IF of step 1. This is <math>\alpha''</math>
 
The new calculated <math>\alpha''</math> will be equally divided across the 3 primary endpoints based on the observed incidence of the 3 case definitions using Pocock rule. If <math>n_1, n_2</math> and <math>n_3</math> are the number of events per CD1, 2 and 3, then the corresponding <math>IF = (n_1/n_3, n_2/n_3, 1)</math> will be used to equally divide <math>\alpha''</math> across the 3 endpoints. The use of the Pocock rule results in equal adjusted significance cut-offs for each CD.
 

		
If Interim Analysis 1 is negative and at the end of the SH RSV season <math>< 18</math> events*
	
If Interim Analysis 2 is positive or Interim Analysis 2 is negative and Conditional Power <math>< 60\%</math> then:

**Table 5: In Case the Study is Performed at the Northern and Southern Hemisphere**

Timepoint/ Number of Events	Interim Analysis 1	Interim Analysis 2	Primary Analysis
	
be divided across the 3 primary endpoints based on the observed incidence of the 3 case definitions using Pocock rule. If <math>n_1</math>, <math>n_2</math> and <math>n_3</math> are the number of events per CD1, 2 and 3, then the corresponding IF= <math>(n_1/n_3, n_2/n_3, 1)</math> will be used to divide <math>\alpha'</math> across the 3 endpoints. The use of the Pocock rule results in equal adjusted significance cut-offs for each CD.
	
are observed a second interim analysis will be conducted (potentially 3 analyses will be performed):
 
 
1. Calculate number of events observed throughout until the end of the SH RSV season (<math>x</math> observed at the time of the interim analysis and <math>n</math> additional events observed until the end of the SH RSV season). In case the study is expanded to a second season (Cohort 2), based on the initial assumptions (2000 additional subjects, with 0.75% RSV incidence and expected 70% VE), 9 additional events are expected during that second season. (Total expected number of events would be <math>x+n+9</math>)
 
2. Given the <math>\alpha'</math> already spent in the 1st interim analysis, the remaining alpha will be equally spent between the second interim analysis and the primary analysis, using a search over a grid of possible <math>\alpha''</math> with IF <math>(x/(x+n+9), (x+n)/(x+n+9), 1)</math>. The grid search will be performed between the interval <math>\alpha'</math> and <math>\alpha</math> (<math>=0.05</math>), initially by steps of size 0.001 (with possible refinement to smaller steps) until the <math>\alpha''</math> at IA2 and PA are equal to each other up to 3 decimal places.
 
3. The new calculated <math>\alpha''</math> will be equally divided across the 3 primary endpoints based on the observed incidence of the 3 case definitions using
 
	
The same <math>\alpha''</math> will be used and equally divided across the 3 primary endpoints based on the observed incidence of each endpoint using Pocock rule. If <math>n_1</math>, <math>n_2</math> and <math>n_3</math> are the number of events per CD1, 2 and 3, then the corresponding IF= <math>(n_1/n_3, n_2/n_3, 1)</math> will be used to equally divide <math>\alpha'</math> across the 3 endpoints. The use of the Pocock rule results in equal adjusted significance cut-offs for each CD.
 
If Interim Analysis 2 is negative and Conditional Power <math>\geq 60\%</math> then:
 
 
1. Calculate number of events observed until the end of the second RSV season (<math>x</math> observed at the time of the first interim analysis, <math>n</math> additional events observed at the end of the SH RSV season and <math>y</math> additionally observed at the end of the second season). Total number of events observed throughout is <math>x+n+y</math>
 
2. The corrected IF of the two interims and the primary analysis is <math>(x/(x+n+y), (x+n)/(x+n+y), 1)</math>.
 
3. Given the <math>\alpha'</math> already spent in the 1st interim analysis and <math>\alpha''</math> has been spent in the 2nd interim analysis, the remaining alpha will be spent using a user defined alpha spending function approach based on <math>\alpha'</math> and <math>\alpha''</math> that were already spent and the corrected IF of step 2. This is <math>\alpha'''</math>
 
4. The new calculated <math>\alpha'''</math> will be equally divided across the 3 primary endpoints based on the observed incidence of the 3 case definitions using Pocock rule. If <math>n_1</math>, <math>n_2</math> and <math>n_3</math> are the number of events per CD1, 2 and 3, then the corresponding IF= <math>(n_1/n_3, n_2/n_3, 1)</math> will be used to equally divide <math>\alpha'''</math> across the 3 endpoints. The use of the Pocock rule results in equal adjusted significance cut-offs for each
 


**Table 5: In Case the Study is Performed at the Northern and Southern Hemisphere**

Timepoint/ Number of Events	Interim Analysis 1	Interim Analysis 2	Primary Analysis
		Pocock rule. If $n_1$ , $n_2$ and $n_3$ are the number of events per CD1, 2 and 3, then the corresponding $IF = (n_1/n_3, n_2/n_3, 1)$ will be used to equally divide $\alpha$ across the 3 endpoints. The use of the Pocock rule results in equal adjusted significance cut-offs for each CD.	CD.
End of SH RSV season / ≥ 18 events* (and no prior IA performed)	No interim analysis	No interim analysis	The Primary analysis will be conducted by the Sponsor:  The full alpha ( $\alpha = 0.05$ ) will be equally divided across the 3 primary endpoints based on the observed incidence of the 3 case definitions using Pocock rule. If $n_1$ , $n_2$ and $n_3$ are the number of events per CD1, 2 and 3, then the corresponding $IF = (n_1/n_3, n_2/n_3, 1)$ will be used to equally divide the alpha across the 3 endpoints. The use of the Pocock rule results in equal adjusted significance cut-offs for each CD.

\* Number of RT-PCR confirmed RSV-mediated LRTD cases (based on Case Definition #2, based on the PPE).

**For example:** assume in a NH and SH study an IA is performed during the SH RSV season with 18 RT-PCR-confirmed RSV-mediated LRTD events observed. RWE data suggests that during the remainder of the SH season a further 8 events would be observed. So, the expected total number of events at the end of the SH season is 26 and the IFs for the interim and primary analyses are 0.7 and 1, respectively. With a total  $\alpha$  of 0.05, the  $\alpha$  at each analysis (IA and primary analysis) will be 0.0335 using Pocock's rule. If then at the IA the total number of events are as follows: 14 events with Case Definition #1, 18 events with Case Definition #2, and 25 events with Case Definition #3, the IFs at the IA are: 0.56, 0.72, and 1. Again, using Pocock's rule, the  $\alpha$  for each individual case definition will be 0.0175. So, proof of concept will be declared at the IA if, for any endpoint, the comparison of the number of events on vaccine compared to placebo if the p-value is  $<0.0175$ .

For sensitivity analyses the corrected alpha level will be used and for the analyses of secondary and exploratory efficacy endpoints a 5% alpha will be used.

#### 4.4.1.1.1. Conditional Power

Based on [Figure 1](#) and [Figure 2](#), there are two occasions that the IDMC will require to evaluate the conditional power. For a NH only study or a NH and SH study, the conditional power is required if at the end of the respective RSV seasons the incidence is exceptionally low (less than 18 observed RT-PCR-confirmed RSV-mediated lower respiratory tract disease (LRTD) events per Case Definition #2, based on the PPE set) and the interim analysis is negative.

The conditional power is calculated as follows:

1. Calculate the significance level at the IA,  $\alpha'$ .
  - Study only performed in the Northern Hemisphere: See *'The Interim Analysis will be conducted by the IDMC'* part in [Table 4](#). Use the significance level resulting from [Table 4](#), step 4 in the corresponding cell.
  - Study performed in the Northern and Southern Hemisphere: see *'If Interim Analysis 1 is negative and at the end of the SH RSV season < 18 events\* are observed a second interim analysis will be conducted (potentially 3 analyses will be performed)'* part in [Table 5](#). Use the significance level resulting from [Table 5](#), step 2 in the corresponding cell.
2. Simulate the number of Case definitions #2 expected at the end of the Season 2, 20000 simulations, assuming 900 additional participants per group (1000 per group assuming a 10% drop out rate), a 0.75% RSV incidence and an expected 70% VE.
3. For each of the 20000 simulations, calculate the adjusted significance level used for the final analysis and use an exact Poisson regression to compare active and placebo:
  - a. Calculate total number of events observed until the end of the second RSV season (x observed at the time of the interim analysis, n number of events simulated for the second season) for each simulation. Total number of events throughout is  $x + n$
  - b. The corrected IF of the interim analysis and the final analysis is  $(x / (x + n), 1)$ .
  - c. Given the  $\alpha'$  already spent in the interim analysis, the remaining alpha will be spent using a user defined alpha spending function approach based on  $\alpha'$  that was already spent and the corrected IF. This will be  $\alpha''$ . Note: for each simulation  $\alpha''$  will be slightly different.
  - d. Use an exact Poisson model to compare active vs placebo, using the total sample size of both seasons and the total number of CD #2 cases across the 2 seasons (observed in season 1 and simulated from season 2). For the Poisson model stratification factors and offsets are not taken into account.
  - e. Keep the one-sided p-value and compare it with the significance level from the previous step for each simulation.
2. Finally, the conditional power is the mean number of cases where the p-values obtained from step 3e is smaller than the significance level obtained from step 3c.

**For example:** assume in a NH only study with 5800 sample size (2900 active and 2900 placebo), at the time of the interim analysis there are in total:

- 5 RT-PCR confirmed RSV-mediated LRTD cases based on Case Definition #2, 4 in the placebo arm and 1 in the active and

Based on [Table 4](#), we expect 9 additional Case Definition #2 events if we expand at season 2, so  $IF=(0.36,1)$  for the interim and final analysis. Using the IF and the Pocock's rule the two planned analysis will be evaluated at a 0.02874 significance level.

After simulating 20000 season 2 scenarios under the CTP assumptions, and performing the simulations, the conditional power is 50 %. The study will not be expanded.

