**Figure 2: Flow Chart in Case the Study is Performed at the Northern and Southern Hemisphere**

a Number of RT-PCR confirmed RSV-mediated LRTD cases (based on Case Definition #2).  
b The study will stop at the end of the RSV season or 6 months after vaccination, whichever comes later.  
 If the number of participants enrolled in the NH is <5,500 but ≥18 RT-PCR-confirmed RSV-mediated LRTD events (using Case Definition #2) are observed in the NH before opening sites in the SH, no sites will be opened in the SH and the study will be performed as a NH study only.  
 CP =conditional power, IA =interim analysis, IDMC =Independent Data Monitoring Committee, LRTD =lower respiratory tract disease, NH =Northern Hemisphere, PA =primary analysis, POC =proof of concept, SH =Southern Hemisphere

So the IDMC will evaluate in an unblinded fashion whether superiority is established for at least one of the primary endpoints (at the early IA or at the end of the RSV season in the event that less than 18 RT-PCR-confirmed RSV-mediated LRTD events are observed) or whether futility (conditional power <60%) is shown for all 3 primary endpoints (at the end of the first RSV season in the event that less than 18 RT-PCR-confirmed RSV-mediated LRTD events are observed).

More details regarding the IDMC roles, responsibilities and way of working are included in the IDMC Charter. This SAP will also be used to support the IDMC analyses. The following sections are applicable for the IDMC analyses: Section 4.2, 4.4.1 and 4.4.2.

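### The conditional-power rule simulates Case Definition 2 alone at the undivided alpha, but futility must hold for all three endpoints and each is tested at the divided level

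*SAP*

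**What the plan says.** Section 3.1 (text after Figure 2) sets the criterion: with fewer than 18 CD2 events at the end of the first season, the IDMC judges whether "futility (conditional power <60%) is shown for all 3 primary endpoints".

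Table 4 (Primary Analysis column, negative interim with conditional power of at least 60%, step 3) fixes the final test. The alpha left after the interim look "will be equally divided across the 3 primary endpoints based on the observed incidence of the 3 case definitions using Pocock rule". Table 5 does the same for the two-hemisphere study. Under Section 4.4.2.2, one endpoint below its cut-off is enough for proof of concept.

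Section 4.4.1.1.1 gives the algorithm. For a Northern Hemisphere study, step 1 reads "Use the significance level resulting from [Table 4](#), step 4 in the corresponding cell". In that cell the division across endpoints is step 5, so the level is taken just before it. For the two-hemisphere study the reference is to Table 5 step 2, again one step before the division. Step 2 is "Simulate the number of Case definitions #2 expected at the end of the Season 2, 20000 simulations". Steps 3a to 3c adjust only for the interim look. Step 3e keeps the one-sided CD2 p-value and tells the reader to "compare it with the significance level from the previous step for each simulation". The worked example uses 0.02874 and CD2 counts only, obtains 50%, and concludes that the study is not expanded.

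**The concern.** There are two separate mismatches.

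- **Endpoint.** The futility criterion needs three conditional powers and the algorithm delivers one. As written, the criterion in Section 3.1 cannot be evaluated.
- **Level.** The simulated test uses the per-analysis alpha. The real test uses roughly half of it for each case definition.

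They pull in different directions. The undivided level overstates the chance that CD2 succeeds. Leaving out CD1 and CD3 understates the chance that at least one endpoint succeeds. At stake is whether 2,000 more participants are enrolled or the study stops.

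**Working it through.** **Inputs, all from the SAP.** Total one-sided alpha 0.05; 9 further CD2 events expected in season 2 (Table 4); 900 per group, incidence 0.75%, VE 70% (Section 4.4.1.1.1, step 2); interim CD2 count 1 active v 4 placebo (worked example). For the three-way split I assume the ratio in the example after Table 5, "14 events with Case Definition #1, 18 events with Case Definition #2, and 25 events with Case Definition #3", which gives information fractions 0.56, 0.72 and 1. Counts below are active v placebo.

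**1. Alpha levels.** The Pocock level a solves 1 − Φ₂(z, z; ρ) = 0.05, with z the upper-a normal quantile and ρ = √(information fraction).
- Fraction 0.36 gives 0.02874, as stated. The unrounded 5/14 gives 0.02871.
- Fraction 0.7 gives 0.0335. The SAP has "at each analysis (IA and primary analysis) will be 0.0335 using Pocock's rule".
- Splitting 0.0335 over 0.56, 0.72, 1 gives 0.0174. The SAP has "for each individual case definition will be 0.0175", a rounding difference.

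**2. The SAP's 50%.** Season-2 placebo cases i follow Bin(900, 0.0075), mean 6.75. Active cases j follow Bin(900, 0.0075 × 0.30 = 0.00225), mean 2.03. For each (i, j), p = P[Bin(5 + i + j, 0.5) ≤ 1 + j], compared with alpha'' re-solved for information fraction 5/(5 + i + j). Summing the probabilities of all significant outcomes gives **49.6%**, matching the stated 50%.

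The figure is sensitive to rounding. At 14 events with 3 active, p = (1 + 14 + 91 + 364)/16384 = 0.02869, which sits on the boundary. Carrying alpha' forward as 0.02874 gives 45.6%.

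**3. Same data, divided level.** The three-way split lowers the level at 14 events to 0.0148, and CD2 conditional power falls to **32.7%**. With other splits it is 32.4% (0.3/0.6/1) and 38.6% (0.8/0.9/1). The stated 50% arises only without the division.

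**4. CD2 results that cross 60%.** Over Northern Hemisphere interims with 4 to 17 CD2 events, none significant on CD2 at the divided level:

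| CD2 | Undivided | Divided |
|---|---|---|
| 0 v 4 | 65% | 54% |
| 1 v 5 | 64% | 43% |
| 1 v 6 | 73% | 54% |
| 2 v 7 | 65% | 50% |
| 3 v 8 | 61% | 43% |
| 3 v 9 | 71% | 54% |
| 4 v 10 | 65% | 45% |
| 4 v 11 | 77% | 56% |
| 5 v 11 | 61% | 42% |
| 5 v 12 | 73% | 54% |

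**5. CD3 at the divided level, CD2 held at 1 v 4.** The SAP gives no CD3 counts or CD3 incidence here. I assume incidence 0.75% × 25/18 = 1.04% and VE 70%. CD3's own conditional power is 65% at 1 v 6, 56% at 1 v 5 and about 39% at 2 v 5. The first case is interim-negative (p = 8/128 = 0.0625), so Section 3.1 would not allow futility, yet the algorithm stops.

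**6. Success on any of the three, divided level, CD2 at 1 v 4.** Simulating nested definitions with VE 70% for each gives:
- about 42% with CD1 1 v 3 and CD3 3 v 6;
- about 66% with CD1 1 v 3 and CD3 1 v 6;
- about 69% with CD1 0 v 3 and CD3 1 v 6.

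The same CD2 data can therefore mean stop or expand.

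**The case against.** The strongest reply is that the rule no longer matters. It acts only with fewer than 18 CD2 events and a negative interim. The current SAP is Amendment 7 of July 2022. It follows Cohort 1 through three seasons, refers to the first-season primary analysis as done, and contains no Cohort 2 analysis, so the expansion branch appears not to have been taken. That stands and limits urgency. It does not make the two sections compatible, and Section 3.1 still names Section 4.4.1 as governing the IDMC analyses.

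Type I error is untouched, because the final test is divided correctly in every branch. That also stands: the defect lies in the forecast.

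The ten splits in the table concern CD2 alone. If CD3 counts were roughly proportional to CD2, CD3 conditional power at the divided level would be about 60% to 85% in most of them, so the all-three rule would usually also say expand. The table shows how far the CD2 figure is overstated; it does not show ten wrong decisions.

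The CD3 counts in step 5 are assumed, and 1 v 5 or 2 v 5 agrees with stopping. The two departures partly offset: any-of-three power of 42% to 69% brackets the SAP's 50%. This rules out a claim of net bias in one direction, but leaves the disagreement dependent on counts the algorithm ignores.

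Finally, CD2 is the SAP's counting event for triggers and information fractions. That explains the choice for timing but does not redefine futility. Figures 1 and 2 and the IDMC Charter, which might say more, are not visible.

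**Conclusion.** The concern holds. Section 4.4.1.1.1 cannot deliver the criterion in Section 3.1, and it tests CD2 at a level the final analysis will not use. In the SAP's example the level alone moves CD2 conditional power from 50% to 33% (32% to 39% across the splits tried). Ignoring the other endpoints can reverse the decision: CD3 at 1 v 6 gives 65%, where the algorithm stops. The CD2 figures rest on the SAP's season-2 assumptions and its 14:18:25 ratio. The CD3 and any-of-three figures rest on assumed counts, scaled incidence and a common VE of 70%. No net direction of bias is claimed.

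**What to change.** In steps 2 and 3 of Section 4.4.1.1.1, simulate the three nested case definitions from the observed interim counts, using the season-2 assumptions and stating those for CD1 and CD3. After step 3c, divide the simulated alpha'' across the three endpoints as in Table 4, step 3, and make the matching change for the two-hemisphere study. Declare futility only if conditional power is below 60% for every definition, as Section 3.1 says. Alternatively, use the probability of success on any of the three and reword Section 3.1 to match. If a CD2-only rule was intended, say so, justify it, amend Section 3.1, and still use the divided level. Recalculate the worked example with counts for all three definitions.

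The cost is SAP wording and a short change to the simulation program, with no extra participants or data.

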#### 4.4.2.2. Analysis Methods

For each of the 3 primary endpoints the following will be performed: an exact Poisson regression will be fitted with the event rate, defined as the number of cases over the follow-up time (offset) as dependent variable and the vaccination group and age and being at increased risk for severe RSV disease (both as stratified) as independent variables. For cases, the follow-up time is defined as the time between vaccination and the occurrence of the first event (according to the considered endpoint), for non-cases, it is the time between vaccination and the end of season visit. In case the EOS visit is missing then the 15th of May 2020 will be used. However, for participants that discontinued before the end of the season and had an event (according to the considered endpoint), the follow-up time is defined as the time between vaccination and the occurrence of the first event and for participants that discontinued before having an event, follow-up time is the time between vaccination and the date of last contact (date of discontinuation).

Note: in case more than one end of season visits are available, the latest will be used to determine the follow up time.

Thus, all participants are included in the analysis according to their follow-up time. The exact one sided p-value corresponding to vaccination group will be compared with the one sided cut-off as described above (Section 4.4.1.1).

If the p-value is below the cut-off for at least 1 of the 3 primary endpoints, proof of concept is demonstrated. The individual exact 2-sided CIs ( $1-2 \times$  cut-off) for the VE (1-relative risk rate), measured by each of the 3 endpoints, will be calculated from the regression model described above and graphically depicted with forest plots.

The primary analysis will be performed on the PPE population, which will take cases into account with an onset at least 14 days after vaccination.

As sensitivity analyses the above Poisson model will be repeated similar to the primary analysis:

- based on the FAS (which also does not take into account the restriction on the onset [at least 14 days] and will count cases from vaccination on Day 1 onwards). RT-PCR results from samples that were out of stability, but tested RSV positive are taken into account in this analysis.
- based on the PPE set but taking into account only RT-PCR test results from the central laboratory (i.e., excluding the local test results for hospitalized participants)

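### The conditional-power algorithm (SAP 4.4.1.1.1) tests Case Definition 2 only, at a level not yet divided over the three endpoints, so it does not compute the futility rule in SAP Section 3.1

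*SAP*

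**What the plan says.** **Decision rule.** SAP Section 3.1, in the text after Figure 2, has the IDMC judge "whether futility (conditional power <60%) is shown for all 3 primary endpoints". The 60% threshold then decides whether 2,000 further participants (Cohort 2) are added. Section 3.1 also lists Section 4.4.1 among the sections that apply to the IDMC analyses.

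**Success rule.** Section 4.4.2.2: "If the p-value is below the cut-off for at least 1 of the 3 primary endpoints, proof of concept is demonstrated".

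**Level at the final test.** Tables 4 and 5 derive α′, α″ or α‴ for the analysis and then split it over the three case definitions before any endpoint is tested: "The use of the Pocock rule results in equal adjusted significance cut-offs for each CD".

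**Algorithm.** Section 4.4.1.1.1 takes its interim level from Table 4 step 4 or Table 5 step 2, both of which come before the split. It then instructs: "Simulate the number of Case definitions #2 expected at the end of the Season 2, 20000 simulations". It tests the CD2 total with an exact Poisson model: "Keep the one-sided p-value and compare it with the significance level from the previous step for each simulation". Read literally, the previous step is 3d, which yields no level; the closing sentence names step 3c, so the level meant is undivided α″. There is no division step and nothing for CD1 or CD3.

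**Information fraction.** Step 3b: "The corrected IF of the interim analysis and the final analysis is" a two-component vector. For a trial that already had a first interim analysis (IA1), Table 5 says "The corrected IF of the two interims and the primary analysis is" a three-component vector.

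**The concern.** Step 3 announces the adjusted level of the final analysis but delivers a larger one, so CD2 conditional power is overstated relative to the test that would be run. Leaving out CD1 and CD3 works the other way. CD3 is the broadest definition and collects the most events, so it may reach 60% when CD2 does not. An IDMC that follows Section 4.4.1.1.1 would hold a number that cannot answer the question Section 3.1 puts to it, and adding 2,000 participants or stopping hangs on that number. With a prior IA1, the algorithm and Table 5 also describe different final levels.

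**Working it through.** **Inputs from the SAP**

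- Total α 0.05, compared with one-sided p-values (Table 4; Section 4.4.2.2).
- Season 2: 900 per group, placebo incidence 0.75%, VE 70%, hence 0.225% on vaccine; 9 further CD2 events expected (Section 4.4.1.1.1; Table 4).
- Worked example: CD2 4 placebo, 1 vaccine; level 0.02874; conditional power 50% (Section 4.4.1.1.1).
- Split over endpoints: 14, 18 and 25 events, IF (0.56, 0.72, 1), borrowed from the example after Table 5, because the conditional-power example gives no CD1 or CD3 counts.

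**Formulas**

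- Pocock level *a*: all Z-statistics fall below z(1−*a*) with probability 1−α, with correlation √(IFᵢ/IFⱼ).
- α″: the final level that brings the total to 0.05, given α′ at the interim and IF x/(x+n).
- With p placebo and v vaccine cases observed and i, j added in season 2, the one-sided p-value is P(X ≤ v+j), X ~ Bin(p+v+i+j, ½).
- Conditional power = Σ Bin(i; 900, 0.0075) · Bin(j; 900, 0.00225) · 1{p-value < level}, enumerated exactly rather than simulated.

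**Step 1: the SAP's own figures.** IF 0.7 gives 0.0335 (SAP 0.0335). Splitting 0.0335 at (0.56, 0.72, 1) gives 0.0174 (SAP 0.0175). IF 0.36 gives 0.02874 (SAP 0.02874). Conditional power for 4:1 with CD2 alone and undivided α″ is 49.6% (SAP 50%). The example therefore confirms how the algorithm is meant to be read.

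**Step 2: the divided level in the same example.** Splitting 0.0287 at (0.56, 0.72, 1) gives 0.0148. With α″ divided in this way for each season 2 total:

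| IF for CD1, CD2, CD3 | CD2 conditional power, 4:1 |
|---|---|
| undivided | 49.6% |
| 0.4, 0.7, 1 | 32.5% |
| 0.56, 0.72, 1 | 32.7% |
| 0.8, 0.9, 1 | 38.6% |
| 0.95, 0.98, 1 | 43.1% |

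Every value is below 60%, so on CD2 the example still ends in no expansion.

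**Step 3: the rule over three endpoints.** The SAP gives no season 2 incidence or VE for CD1 and CD3. Assumed here: incidence scaled 14:18:25, so CD1 0.75% × 14/18 = 0.583% and CD3 0.75% × 25/18 = 1.042%; VE 70% for each; α″ at the expected 9 events, then divided.

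| Placebo:vaccine at interim (CD1, CD2, CD3) | As written | CD1, CD2, CD3 at divided level | Section 3.1 |
|---|---|---|---|
| 4:1, 5:1, 6:2 | 64%, expand | 24%, 43%, 49% | futile on all three |
| 3:1, 4:1, 6:1 | 50%, stop | 15%, 33%, 65% | not futile |

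The second row is fragile: CD3 falls to 54% if its incidence is 0.75%, and to 51% at incidence 1.042% with VE 60%.

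**Step 4: path with a prior IA1.** Illustration: IA1 at 14 events with 8 more expected (the 8 is borrowed from the example after Table 5), then 17 events (12:5) at the end of the Southern Hemisphere season.

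- IF 14/22 gives α′ = 0.0324.
- Table 5 step 2 with IF (14/26, 17/26, 1) gives a nominal α″ of 0.0234; cumulative spend through the second interim is 0.0392.

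| How step 3 is run (9 further events for the level) | Final level | CD2 conditional power, undivided |
|---|---|---|
| Two-component IF, 0.0234 entered as spent | 0.0405 | 77% |
| Two-component IF, 0.0392 entered as spent | 0.0253 | 64.5% |
| Table 5, three-component IF | 0.0234 | 63.6% |

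The wording of step 3c does not settle which of the first two rows applies.

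**The case against.** **CD2 may be the intended index.** Section 4.4.1.1 says that an event in Tables 4 and 5 means a CD2 case, and the 14, 18 and 9 event counts are all CD2. A CD2-based futility measure may be deliberate. That stands as a route to reconciliation, since Section 3.1 could be reworded. It does not explain the undivided level.

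**Apparent reversals on CD2 alone.** A reader might infer from CD2 that the algorithm wrongly expands the trial: 5:1, 7:2 and 11:5 give 64%, 65% and 61% as written but 43%, 50% and 42% at the divided level. The documents do not support that inference, because under Section 3.1 CD2 below 60% is not futility. With the Step 3 assumptions, 7:2 accompanied by CD3 9:3 gives about 65% on CD3, and 11:5 with CD3 15:7 gives 65% to 66%. Neither is futile, in agreement with the algorithm. Undivided CD2 can thus be a fair proxy for the three-endpoint rule, though not reliably, as the first row in Step 3 shows.

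**Alpha spent at IA1.** A reader might also infer that the algorithm ignores it. Table 5 step 2 already conditions on it. Its grid search runs from α′ to 0.05, which contains the cumulative 0.0392 but not the nominal 0.0234. On the cumulative reading almost all of the gap in Step 4 disappears.

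**Reach.** Conditional power does not enter the efficacy cut-offs, and it is used only with fewer than 18 CD2 events and a negative interim. Section 1.6 treats the first-season primary analysis as done. All of this stands and lowers the severity.

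**Conclusion.** The point holds as an inconsistency between a stated decision rule and its only algorithm. Section 4.4.1.1.1 covers one endpoint of three and uses a level that the final test would not use. In the SAP's example the level alone moves CD2 conditional power from 50% to about 33% (32% to 43% over the ratios tried), without changing the decision on CD2.

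That the expand-or-stop decision is generally reversed is not shown. It can move either way under the Step 3 assumptions, and the SAP supplies no CD1 or CD3 figures to say how often. For the path with a prior IA1, the mismatch in information fractions is real; its effect runs from negligible (64.5% against 63.6%) to material (77% against 63.6%) according to how step 3c is read.

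Severity is moderate: type I error and efficacy cut-offs are untouched, and the branch is narrow.

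**What to change.** 1. In steps 3c to 3e, compare each simulated p-value with α″ after division over the three case definitions, as in Tables 4 and 5. When IA1 was done, use α‴ with the three-component information fraction, and state whether the α entered is a nominal level or a cumulative spend.
2. Reconcile Sections 3.1 and 4.4.1.1.1. Either compute conditional power for each case definition (or for success on at least one), with season 2 incidence and VE for CD1 and CD3 written down, or reword Section 3.1 as a CD2-based rule.
3. Recompute the worked example and show the CD1 and CD3 counts used for the division.

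Cost: SAP wording, simulation code, some additional stated assumptions, and a CD2 conditional power that looks less favourable. No data collection changes.
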